#### 11.1.1. Screening Design

In the screening phase, a Bayesian continuous futility monitoring rule will be implemented based on the rate of CR plus CRi in each of the 3 arms of the AML stratum, respectively. An arm will be stopped if Prob (CR+CRi > 25% | data) < 0.05. The above stopping rule suggests that, given the data obtained from patients who have already been evaluated in an arm, if there is less than a 5% chance that the rate of CR+CRi is greater than 25% we will terminate the arm. This decision rule generates the following stopping boundaries, assuming a beta(1,1) prior distribution for the response (CR+CRi) rate in each arm. Stop an arm i if [ # of pts with CR or CRi in arm i / # of pts evaluated in arm i ]  $\leq$  0/10, 1/17, where i = 1, 2, or 3. The operating characteristics of this rule are shown in Table 8.

Table 8 Operating Characteristics of Futility Monitoring - Maximum 20 AML Patients

		Sample Size		
Rate of CR or CRi	Probability of stopping	P 25	P 50	P 75
0.05	0.822	10	10	17
0.10	0.54	10	17	20
0.15	0.313	17	20	20
0.20	0.165	20	20	20
0.25	0.082	20	20	20
0.30	0.039	20	20	20

After treating up to 10 evaluable AML patients defined as patients who have completed at least 1 cycle of treatment at each dosing schedule

- If no CR or CRi is observed, declare the treatment insufficiently active and no more AML patient will be treated with this dose regimen
- If at least one CR or CRi is observed, add AML patients to reach a total of 17 patients and
  - o If less than two CR plus CRi are observed, declare the treatment insufficiently active
  - o If at least two CR and CRi are observed, add AML patients to reach a maximum of 20 patients

For both AML and MDS patients, there is an early stopping rule for excessive toxicity. A dosing schedule will be declared to have excessive toxicity and no more patients will be treated with this dose regimen if among the first 10 patients treated with this dose regiment in either the AML or MDS stratum, there are > 2 patients experienced serious adverse events (excluding simple complications associated with myelosuppression such as neutropenic fever without shock or its complications from gram-negative bacteremia, anemia or mucosal bleeding, *e.g.*, epistaxis, due to thrombocytopenia easily controlled by transfusion) that are considered by investigator to be definitely, probably or possibly related to the study drug during the first two treatment cycles.

If a dosing schedule within the AML stratum has at least 4 CR and CRi, and the 30-day death rate is 20% or less, additional AML patients may be added to confirm the safety and tolerability of that dosing schedule. If a dosing schedule within the MDS stratum has at least 4 CR, CRp, PR, and major HI, and the 30-day death rate is 20% or less, additional MDS patients may be added to confirm the safety and tolerability of that dosing schedule.

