### 3.3. Rationale for the Proposed Dosing Schedules

Preliminary pharmacokinetic analyses from two completed phase I studies indicate that sapacitabine and its active metabolite CNDAC have a relatively short half-life (approximately 2 hours) and that CNDAC exposure appears to correlate with the worst NCI-CTC grade of neutropenia experienced during treatment at the MTD. We hypothesize that the 7-day high dose regimen will lead to higher dose delivered per week (1400 mg/week) resulting in better antitumor activity than the 7-day low dose regimen (933 mg/week) but may cause more myelosuppression; the 3-day high dose regimen will have higher dose delivered per week (1600 mg/week) resulting in better anti-tumor activity than the 7-day high dose regimen but will have similar degree of myelosuppression and gastrointestinal toxicity because the consecutive days of dosing are shorter. Preliminary data from the 60 patients in the original cohort of the AML stratum showed that the dosing schedule of 400 mg b.i.d. x 3 days/week x 2 weeks every 3-4 weeks has the highest rate of CR/CRp, i.e., 25%, the longest durations of responses, and a 10% all-cause death rate within the first 30 days after randomization. However, all patients who achieved CRs were dose reduced for myelosuppression. We hypothesize that a 3-day dosing regimen of 300 mg b.i.d. x 3 days/week x 2 weeks every 4 weeks will be equally effective but with less myelosuppression and propose to test this dosing regimen in Part 2 of the study. Exploratory subgroup analyses from AML patients enrolled in Part 1 of the study suggest that the 7-day low dose schedule of 200 mg b.i.d. x 7 days every 3-4 weeks (Arm A) may be more effective for AML preceded by MDS or MPD. Among 7 patients on Arm A who have survived at least 1 year, 4 patients have AML preceded by MDS or MPD. We hypothesize that a 7-day once daily (q.d.) dose regimen and a lower dose of the 3-day dose regimen may be equally effective but with less myelosuppression. We propose to evaluate 300 mg a.d. x 7 days and 300 mg b.i.d.

x 3 days/week x 2 weeks every 4 weeks in patients with newly diagnosed AML preceded by MDS after receiving hypomethylating agents for the preceding MDS (Part 3).

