#### 9. EFFICACY ASSESSMENT

The primary efficacy endpoint of Part 1 of this study is 1-year survival, i.e., the proportion of patients who are alive at 1-year measured from the date of the randomization. Secondary efficacy endpoints are the rate of CR, CRp, PR or CRi or hematological improvement and their corresponding durations, transfusion requirements and number of hospitalized days. The primary efficacy endpoints of Part 2 of this study are the rate of clinical benefit response (CR, CRp, PR, or major HI) and the rate of complete response (CR or CRp). Secondary efficacy endpoints are response durations, transfusion requirements, number of hospitalized days, and overall survival. The primary efficacy endpoint of Part 3 and 4 of this study is 1-year survival rate. Secondary efficacy endpoints are the rate of clinical benefit response (CR, CRp, PR, major HI or SD) and their corresponding durations, transfusion requirements, number of hospitalized days and overall survival.

The tissue samples supporting the diagnosis of AML or MDS, and the responses to sapacitabine may be submitted for central review.

Table 6 Response Criteria

Passansa Description					
Response	Description				
Complete Remission (CR) 	Normalization of peripheral neutrophils to ≥1000 /µL, platelet to ≥100,000/µL within 2 weeks of bone marrow biopsy/aspirate, and bone marrow to ≤5 % blasts; independent of transfusions*; and no extramedullary leukemia.				
Complete remission with incomplete platelet count recovery (CRp) 	Normalization of bone marrow to $\leq$ 5% blasts; peripheral neutrophils $\geq$ 1000 /µl, platelet $<$ 100,000 /µL within 2 weeks of bone marrow biopsy/aspirate; independent of transfusions*; and no extramedullary leukemia.				
Complete remission with incomplete blood count recovery (CRi) 8	Normalization of bone marrow to $\leq$ 5% blasts; peripheral neutrophils $<1000~/\mu$ L, platelet $<100,000/\mu$ L within 2 weeks of bone marrow biopsy/aspirate; independent of transfusions *; and no extramedullary leukemia.				
Partial Remission (PR) 8	Normalization of peripheral neutrophils to $\geq 1000 \ / \mu L$ , platelet to $\geq 100,000/\mu L$ within 2 weeks of bone marrow biopsy/aspirate, $\geq 50\%$ decrease in bone marrow blasts over pretreatment but still >5%; independent of transfusions * .				
Hematological improvement (HI) 9	Major response:				

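### The Part 1 AML screening, expansion and separate-analysis rules count CR and CRi but do not name CRp, so read literally they score CRp patients as failures

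*Combined protocol and SAP*

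**What the plan says.** Section 11.1 makes CR plus CRi the measure of activity for AML in Part 1, and the selection step presupposes schedules found active on it. Section 11.1.1 applies a Bayesian futility rule "based on the rate of CR plus CRi in each of the 3 arms of the AML stratum": "An arm will be stopped if Prob (CR+CRi > 25% | data) < 0.05", "assuming a beta(1,1) prior distribution for the response (CR+CRi) rate in each arm". The resulting boundaries are 0/10 and 1/17. At 10 evaluable patients, "If no CR or CRi is observed, declare the treatment insufficiently active and no more AML patient will be treated with this dose regimen". At 17, "If less than two CR plus CRi are observed, declare the treatment insufficiently active".

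The expansion trigger at the end of Section 11.1.1 keeps the same count: "If a dosing schedule within the AML stratum has at least 4 CR and CRi", together with a 30-day death rate of at most 20%. Section 11.4 analyses additional patients separately when a schedule has reached 20% CR/CRi.

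Table 6 in Section 9 gives CRp and CRi separate rows with the same blast, transfusion and extramedullary conditions. CRp has neutrophils of at least 1000 and platelets below 100,000. CRi has neutrophils below 1000 and platelets below 100,000, joined by a comma.

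Elsewhere CRp counts as activity:
- the MDS expansion trigger, also in Section 11.1.1
- complete response in Part 2 (Section 11.2)
- clinical benefit in Parts 3 and 4 (Section 11.3.1)
- Section 3.3, where the 400 mg 3-day schedule "has the highest rate of CR/CRp, i.e., 25" percent

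**The concern.** CRp and CRi differ only in count recovery, and on the text CRp is the better of the two. A rule that credits CRi and omits CRp ranks responses the wrong way round. No section says that CRi includes CRp, and none gives a reason for leaving CRp out. The MDS trigger and the clinical benefit definition do the reverse: they name CRp and not CRi. Section 3.7 lists CRp and CRi as separate investigator assessments on the case report form, so someone who counts the CR and CRi entries would leave the CRp patients out.

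Three decisions depend on the count: whether an AML schedule is declared active and can enter selection, whether it qualifies for additional patients, and whether those patients are analysed separately. Two readers with the same data could reach different answers on each.

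**Working it through.** **Inputs.** From Section 11.1.1: beta(1,1) prior, 25% threshold, 0.05 cut-off, looks at 10 and 17, maximum of 20 per arm, trigger of at least 4 responses. The share of CRp among all CR, CRp and CRi responders is not in the documents, so it is an assumption and is varied.

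**1. Boundaries.** With x responses in n, the posterior is Beta(1+x, 1+n−x). The probability that the rate exceeds 25% is:
- 0/9: 0.0563; 0/10: 0.0422
- 1/16: 0.0501; 1/17: 0.0395

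The boundaries 0/10 and 1/17 are confirmed.

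**2. Table 8.** With p the rate of *counted* responses, an arm stops with 0 of 10, or with exactly 1 of 10 and then 0 of the next 7:

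P(stop) = (1−p)^10 + 10·p·(1−p)^9·(1−p)^7 = (1−p)^10 + 10·p·(1−p)^16

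| p | Recomputed | Table 8 |
|---|---|---|
| 0.05 | 0.819 | 0.822 |
| 0.10 | 0.534 | 0.54 |
| 0.15 | 0.308 | 0.313 |
| 0.20 | 0.164 | 0.165 |
| 0.25 | 0.081 | 0.082 |
| 0.30 | 0.038 | 0.039 |

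All rows agree within 0.6 percentage points. Table 8 is right for whatever response is counted; the open question is which responses are counted.

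**3. Effect of omitting CRp.** If the total remission rate is T and a share s of responders are CRp, the counted rate is p = T(1−s). For T = 25% and s = 40%, p = 0.15:

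P(stop) = 0.85^10 + 10 × 0.15 × 0.85^16 = 0.1969 + 0.1114 = 0.308

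With CRp counted, p = 0.25:

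P(stop) = 0.75^10 + 10 × 0.25 × 0.75^16 = 0.0563 + 0.0251 = 0.081

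**4. Expansion trigger.** The probability of passing both looks and reaching at least 4 of 20 is the plain binomial probability less the paths already stopped:

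P = P(X≥4 of 20) − (1−p)^10·P(X≥4 of 10) − 10·p·(1−p)^16·p^3

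- p = 0.25: 0.7748 − 0.0563 × 0.2241 − 0.0251 × 0.25^3 = 0.762
- p = 0.15: 0.3523 − 0.1969 × 0.0500 − 0.1114 × 0.15^3 = 0.342

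The 30-day death condition is ignored.

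**5. Range.**

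| CRp share | Counted rate, T = 25% | P(stop) | P(pass, at least 4 of 20) | P(stop), T = 30% | P(pass, at least 4 of 20), T = 30% |
|---|---|---|---|---|---|
| 0% | 0.25 | 0.081 | 0.762 | 0.038 | 0.883 |
| 20% | 0.20 | 0.164 | 0.575 | 0.094 | 0.730 |
| 40% | 0.15 | 0.308 | 0.342 | 0.213 | 0.485 |
| 60% | 0.10 | 0.534 | 0.128 | 0.434 | 0.206 |

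The 0% row is also the result for any share once CRp is counted.

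**6. What is still open.** Section 3.3 reports on 60 patients in the original AML cohort. Three arms at the maximum of 20 make 3 × 20 = 60, which suggests that no arm stopped early. Section 3.4 plans about 100 AML patients in Part 1, so about 100 − 60 = 40 lie beyond that cohort, where the expansion and separate-analysis rules apply.

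**The case against.** **Futility stops.** A reader might infer that active arms have been, or will be, wrongly stopped. The documents do not support that. A 60-patient original cohort implies three full arms, so the stopping probabilities mostly describe decisions already taken. This objection stands.

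**Expansion.** A reader might also infer that a schedule was denied expansion. The trigger only permits more patients, and Section 3.4 already plans about 40 beyond the original 60. Nothing shows that any arm was refused. This stands too, although the rule still governs how expansion is justified.

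**Meaning of CRi.** The CRi row joins its two count conditions with a comma. Read as 'and', it leaves no remission category for a patient with low neutrophils but recovered platelets. Read as 'or', it closes that gap and takes in CRp. The end of Section 6.2 describes clinical benefit as CR, CRi or SD without CRp, which fits CRi as an umbrella term. That reading is possible, so it goes too far to say that CRp is certainly excluded. Against it, Sections 3.7, 9, 11.1 and 11.4 list CRp and CRi side by side as different outcomes. If the umbrella meaning was intended, it still has to be stated.

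**Late change.** The trial is open label and responses by arm are known. If CR plus CRi was meant literally, adding CRp now widens the response held to the same 25% threshold after data were seen. This stands as a cost of the fix.

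**Reporting.** The primary endpoint is 1-year survival, and CRp is reported with its own confidence interval under Section 11.4. No CRp response is lost from the results; only the decision rules are affected.

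**Conclusion.** The point holds as a defect in the definition of the counted response. As written, the Part 1 AML rules credit CRi and do not credit CRp, contrary to the ordering in Table 6 and to the protocol's use of CRp elsewhere. The boundaries and Table 8 are correct.

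The size depends wholly on the unreported CRp share. At a 25% total rate, a share of 20% to 60% takes the stopping probability from 0.081 to between 0.164 and 0.534. It takes the probability of passing screening with 4 counted responses from 0.762 to between 0.575 and 0.128. With no CRp responders nothing changes. These figures assume a literal reading of the rule, independent patients with a common rate, and no effect of the 30-day death condition.

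The effect that remains is on the activity verdict before selection, the at-least-4 trigger and the 20% separate-analysis rule. That the futility looks are past is an inference from the cohort size; the documents do not state it. The point should be corrected, but it is not evidence that any arm was mishandled.

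**What to change.** State the counted response as 'CR, CRp or CRi' in Section 11.1 (purpose and selection precondition), Section 11.1.1 (stopping rule, both boundary bullets, Table 8 label and expansion trigger) and Section 11.4 (20% rule). Alternatively, define CRi in Table 6 to include CRp and use that definition in all of these places. Keep the boundaries 0/10 and 1/17 and the Table 8 probabilities, which hold for whatever response is counted.

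Sample size and data collection do not change, since CRp is already assessed. The one real cost is timing. The amendment should record when the change was made and which count was applied to the original 60 patients, and the report should give the count for each arm with and without CRp.

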#### 11.1.2. Selection Design

Assuming that at least 2 dosing schedules show activity and that their toxicity profile is similar, a selection design will be used to choose the dosing schedule with the better observed 1-year survival rate. If the better dosing schedule has a true 1-year rate of 45% and the worse dosing schedule a true 1-year rate of 30%, the trial has better than 80% probability to choose the correct dosing schedule if 20 patients have been treated with each dosing schedule.

No formal hypothesis testing will be carried out for the 1-year survival rate. Instead, we will estimate the 1-year survival rate for each dosing schedule, along with the 95% confidence interval. Given a total of 20 patients in an arm and assuming a 1-year survival rate of 45%, the half-width of the 95% confidence interval will be 0.22. On the other hand, if assuming a 1-year survival rate of 30%, the half-width of the 95% confidence interval will be 0.20.

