#### 11. BIOSTATISTICAL CONSIDERATIONS

### 11.1. Sample Size for Part 1 of the Study

This study is an open-label, randomized study of 3 dosing schedules of sapacitabine. The primary objective of this study is to evaluate 1-year survival rate of 3 dosing schedules in elderly patients with previously untreated or first relapsed AML or previously treated MDS; the secondary objectives are to assess the number of patients who have achieved a CR, CRp, PR or CRi or hematological improvement and their corresponding durations, transfusion requirements, number of hospitalized days and safety.

The primary efficacy endpoint is 1-year survival measured from the date of randomization. Statistically, the purpose of the trial is to reject the dosing schedules from further study if they were insufficiently active based on the rate of CR plus CRi for AML, and to accept them for further study if they were truly active. This will not apply to the MDS stratum because the CR rate of standard therapy by hypomethylating agents is only 6-9% and there is no effective therapy for those who have been previously treated by hypomethylating agents. For "screening" purpose, a Bayesian continuous futility monitoring rule is used for each dose schedule separately based on the rate of CR plus CRi for AML, and a "selection" design to choose the better dosing schedule based on 1-year survival rate if all 3 dosing schedules are found to have activity based on the rate of CR plus CRi. This randomized phase II trial is not expected to have sufficient power to compare the 3 dosing regimens on the basis of 1-year survival rate.

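### The better-than-80% chance of correct selection holds for two schedules; with three, at assumed rates of 45%, 30% and 30%, it is about 74% (ties broken at random)

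*Combined protocol and SAP*

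**What the plan says.** Section 11.1.2 describes a selection design that picks the schedule with the better observed 1-year survival rate. Its assumptions are: "If the better dosing schedule has a true 1-year rate of 45% and the worse dosing schedule a true 1-year rate of 30" percent. On these it concludes that "the trial has better than 80% probability to choose the correct dosing schedule if 20 patients have been treated with each dosing schedule". Section 11.3.2 repeats the statement for Parts 3 and 4.

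The sections differ on when selection applies. Section 11.1 says the design is used to "choose the better dosing schedule based on 1-year survival rate if all 3 dosing schedules are found to have activity", and Section 11.3 uses the same condition for Parts 3 and 4. Sections 11.1.2 and 11.3.2 open instead with "Assuming that at least 2 dosing schedules show activity and that their toxicity profile is similar".

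Sections 3.1 and 6.1 give three schedules in each randomized part. The plan states no true rate for a third schedule, no rule for ties, and no selection probability for three schedules.

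**The concern.** The statement names one better and one worse rate, so its arithmetic is that of a two-schedule contest. Yet it is worded as a property of the trial, with 20 patients on each schedule, and it is the only operating characteristic the plan gives for the selection step. With a third contender, the best schedule has to beat two others by chance as well as by merit, and its probability of finishing first falls unless the third is clearly inferior.

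Choosing a schedule for further development is the stated rationale of the study (Section 1.5). A reader who accepts the figure will put the risk of a wrong choice below 20%. If three schedules compete, the risk may be materially higher, and nothing in the plan says so.

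**Working it through.** **Inputs.** From Section 11.1.2: "If the better dosing schedule has a true 1-year rate of 45" percent, "the worse dosing schedule a true 1-year rate of 30" percent, and "if 20 patients have been treated with each dosing schedule". The rule is to pick the highest observed 1-year survival. The third schedule's rate is not in the documents; it is taken as 30% (the plan's own worse rate) and then varied. Survivor counts are treated as independent binomials with n = 20: X₁ for the 45% schedule, X₂ for the 30% schedule, X₃ for the third.

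**Step 1: the plan's own figure, two schedules.**

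P(correct) = P(X₁ > X₂) + ½ P(X₁ = X₂) = 0.7965 + ½ × 0.0798 = 0.836.

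A normal approximation gives 0.839. The plan's figure is reproduced. If a tie is not counted as a correct choice, the result is 0.796, just under 80%.

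**Step 2: three schedules.** With ties shared equally among the leaders, sum over x from 0 to 20:

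P(correct) = Σ P(X₁ = x) × [P(X₂ < x) P(X₃ < x) + ½ P(X₂ = x) P(X₃ < x) + ½ P(X₂ < x) P(X₃ = x) + ⅓ P(X₂ = x) P(X₃ = x)].

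| Tie rule | Two schedules (45/30) | Three schedules (45/30/30) |
|---|---|---|
| Split at random | 83.6% | 74.0% |
| Tie not counted as correct | 79.6% | 68.5% |
| Every tie goes to the best | 87.6% | 79.7% |

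Simulation of the split-tie, three-schedule case (1,000,000 runs) gives 73.9%. At 45/30/30 the result is below 80% under all three tie rules.

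**Step 3: sensitivity to the assumed third rate** (45% and 30% fixed, ties split).

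| Third rate | P(best is chosen) |
|---|---|
| 10% | 83.5% |
| 20% | 81.7% |
| 25% | 78.9% |
| 30% | 74.0% |
| 35% | 66.7% |
| 37.5% | 62.3% |
| 40% | 57.4% |

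The 80% line is crossed at a third rate of 23.4%. If every tie goes to the best schedule, the crossing moves to 29.8%.

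**Step 4: how often three schedules would compete.** Using the stopping probabilities in Tables 8 and 9, and assuming independent arms with the same response rate and no toxicity stops, the chance that all three pass the futility screen is:

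- 20% response rate: (1 − 0.165)³ = 0.58
- 25% response rate: (1 − 0.082)³ = 0.77
- 30% response rate: (1 − 0.039)³ = 0.89

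For the Part 1 MDS stratum, Section 11.1 says of the response-based screen: "This will not apply to the MDS stratum because the CR rate of standard therapy by hypomethylating agents is only 6-9" percent. Futility therefore never reduces three schedules to two there.

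**The case against.** The strongest reply is that the sentence is correct as written. It speaks of a better and a worse schedule, gives two rates, and follows a condition of at least two active schedules. On that reading a second scenario has been left out, but no number is wrong. The shortfall also depends on a rate the plan never gives. This stands in part: the two-schedule figure is right, and the claim survives a sufficiently poor third schedule. But the sentence carries no two-schedule label, and Sections 11.1 and 11.3 name the three-schedule case. Keeping 80% there, with ties split, needs a third rate nearly 7 points below the plan's own worse rate.

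A second reply is that the low end of the sensitivity range overstates the harm, because many wrong picks are then the near-best schedule. This is true. With a third rate of 40%, the chance of ending up with the 30% schedule is 8.7%, against 16.4% in the two-schedule contest. The 45/30/30 case gets no such relief: both alternatives are 15 points worse, and one of them is chosen 26% of the time.

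Third, the pass rates in Step 4 are generous. They ignore toxicity stops and the requirement of similar toxicity profiles, and Part 1 MDS has no stated activity criterion for entering selection. They show that three competing schedules are plausible and should not be read as forecasts.

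Finally, Sections 11.1 and 11.3 disclaim adequate power to compare the regimens, and no formal test is planned. That limits what rests on the figure. But power to compare and probability of correct selection are different quantities, and the disclaimer does not correct the second.

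**Conclusion.** The concern holds. The stated probability is right for two schedules (83.6%, ties split) and is not supported for three unless the third is assumed to be clearly inferior. At 45/30/30 with 20 patients each, the probability is 74.0%, or 68.5% to 79.7% depending on the tie rule. The risk of a wrong choice is then about 26% with ties split, against 16% for two schedules.

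These figures assume independent binomial counts, full 1-year follow-up, and 20 patients on every schedule that reaches selection. The third rate is an assumption of this review. The conflict between requiring all three active schedules and requiring at least two is a separate, real inconsistency: it leaves open whether selection applies when exactly two are active. The futility tables, the confidence-interval half-widths and the sample size are unaffected. What changes is how much confidence the selection deserves. This should be fixed.

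**What to change.** In Sections 11.1.2 and 11.3.2, replace the single figure with two labelled ones, along these lines: *If two schedules remain, with true 1-year rates of 45% and 30%, 20 patients each give about 84% probability of choosing the better one, ties broken at random. If three remain, the probability is about 74% assuming rates of 45%, 30% and 30%, and ranges from about 84% to 62% as the third rate goes from 10% to 37.5%.* It would be fair to add that at the high end of that range most wrong picks are the near-best schedule.

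State the tie rule. Use one condition for applying selection, either all three active or at least two, in Sections 11.1, 11.1.2, 11.3 and 11.3.2.

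The cost is wording only, plus a less favourable stated probability for three schedules. No patients are added. For scale, exceeding 80% at 45/30/30 with ties split would take 29 per schedule (28 give 79.9%, 29 give 80.5%), but this review does not ask for that. The change is prospective for Parts 3 and 4. Section 3.3 already reports data from both Part 1 strata, so there it affects only how the selection is reported.
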